7.2.3 Diarrhea

Grade 1 or 2

TDF/FTC may be continued without interruption. Subjects with diarrhea of any toxicity grade may be treated symptomatically with permitted antimotility agents.

Grade 3 or 4

For grade 3 diarrhea that is unresponsive to antimotility agents and for which an alternative etiology (e.g., infectious diarrhea) is not established, TDF/FTC should be interrupted until resolution of diarrhea to Grade ≤ 2 or baseline. If Grade ≥ 3 diarrhea recurs upon the resumption of study medications, TDF/FTC should be permanently discontinued. Grade 4 will lead to permanent discontinuation of study medication.

7.2.4 Hyperglycemia

Fasting hyperglycemia of > 110 to 125 mg/dL is considered evidence of impaired glucose tolerance. A fasting blood glucose level above 126 mg/dL is highly suggestive of diabetes mellitus. Subjects with fasting hyperglycemia may continue TDF/FTC at the discretion of the investigator but should be discussed with the protocol team via email. A confirmatory fasting glucose will be obtained within 4 weeks and prior to the institution of medical therapy. Hyperglycemia may be treated with oral hypoglycemic agents or insulin according to standard guidelines. Abnormal glucose levels will be monitored closely, and further laboratory repeats will be at the discretion of the site PI.

7.2.5 AST/ALT Elevations

Grade 1 or 2

TDF/FTC may be continued. Tests should be repeated and reassessed within 2 weeks if AST/ALT results are \geq grade 2

Grade 3

All grade 3 or 4 elevations of AST/ALT should be discussed immediately with the protocol team via email. TDF/FTC may be continued for Grade 3 AST/ALT elevations at the discretion of the site investigator after discussion with the protocol team. Careful assessments should be done to rule out the use of alcohol, non-study medication-related drug toxicity, or viral hepatitis as the cause of the Grade 3 elevation.

Grade 4

TDF/FTC will be permanently discontinued for AST or ALT Grade 4 elevations, and the protocol team will be notified. The subject should have repeated AST or ALT evaluations until the levels have returned to $<$ grade 2 or baseline. Once the AE is resolved, the subject should be

followed on-study, but off study medication.

7.2.6 Creatinine Elevations

TDF/FTC will be discontinued if the creatinine clearance is confirmed to be < 50 mL/min. Subjects should be followed as medically indicated until the creatinine returns to baseline. The protocol team will be notified within 48 hours of any permanent therapy discontinuations due to change in creatinine clearance.

If the serum creatinine increases more than 0.3 from baseline, the level should be repeated in 2 weeks. Elevations in creatinine will be monitored closely, and further laboratory repeats will be at the discretion of the site PI.

7.2.7 Anemia/Neutropenia

Subjects with Grade 3 anemia or neutropenia attributed to TDF/FTC should have all study treatment interrupted until the abnormality returns to Grade \leq 2. Therapy may be resumed after the anemia or neutropenia has returned to Grade \leq 2. If Grade 3 anemia or neutropenia recurs, TDF/FTC will be discontinued, and the protocol team will be notified.

Grade 4 anemia or neutropenia will result in permanent discontinuation of study medication if it is due to TDF/ FTC.

8.0 CRITERIA FOR TREATMENT DISCONTINUATION

8.1 Criteria for Discontinuation from Study

- 8.1.1 Diagnosis of HIV infection.
- 8.1.2 Request by the subject to withdraw.
- 8.1.3 Request of the primary care provider if s/he thinks the study is no longer in the best interest of the subject.
- 8.1.4 Clinical reasons believed life threatening by the study physician, even if not addressed in the toxicity management of the protocol, and can no longer continue in follow up.
- 8.1.5 Subject judged by the investigator to be at significant risk of failing to

comply with the provisions of the protocol as to cause harm to self or seriously interfere with the validity of the study results.

- 8.1.6 At the discretion of the CCTG, FDA, CHRP or pharmaceutical sponsors.
- 8.1.7 Misses two consecutive scheduled visits prior to 48 weeks.
- 8.1.8 Misses one scheduled visit after 48 weeks.

9.0 STATISTICAL CONSIDERATIONS

A formal Statistical Analysis Plan (SAP) will be drafted and finalized prior to database lock. The SAP will contain a more detailed and/or comprehensive presentation of statistical methods, attention to any changes of substance to planned analysis procedures relative to those indicated in the protocol, and is the final authority for all statistical analyses. The following section briefly describes the planned statistical analyses. In case the language in this section differs from the language in the SAP, the SAP takes precedence.

9.1 Primary Endpoints

Adherent to PrEP through 48 weeks is defined as a composite endpoint of continuing on study (made all scheduled visits within window in the 48 week period) and on study medication and greater than or equal to 90% adherent to medication defined by self-report of ≥ 18 of 20 doses of medication on the 5 ACTG adherence questionnaires at weeks 4, 12, 24, 36 and 48. Missing adherence forms will be imputed as no doses taken.

9.2 Secondary Endpoints

- 9.2.1 Adherent to PrEP by FTC measurement at 48 weeks and at the end of study follow-up is defined by attending all scheduled visits and having detectable FTC.
- 9.2.2 Adherent to PrEP in continuous follow up is aggregate percentage of self-reported ACTG days of adherence where missed schedule visits are counted as 0/4 days.
- 9.2.3 Poor adherence is considered those with <90% self-reported adherence by ACTG 4 day survey or if discontinued drug. Subgroup analysis should explore the endpoint for discontinuation for reasons other than quit drug for lack of risk or confirmed adverse event.
- 9.2.4 Safety and tolerability defined as: i) discontinuation of TDF/ FTC for any

toxicity; ii) grade 2 or higher adverse event or laboratory toxicity; iii) serious adverse event; iv) death

9.3 Randomization and Stratification

We will conduct an open-label, randomized, controlled, two-arm, clinical strategy trial for PrEP adherence. Subjects will be randomized (1:1) to one of two arms: the **Standard of Care** (SoC) or the **iTAB** enhanced adherence arm. Randomization will be stratified by clinic site. A total of 400 subjects (200 per arm) will be randomized and followed in the study for 48 weeks after enrollment of the last subject.

Once eligibility and consent are confirmed, randomization will occur using the web-based CFAR BIT data management system.

9.4 Study Power and Sample Size Justification

The primary objective for this study is to compare the proportion of subjects that reach the composite endpoint, defined as: continued retention and adherence to PrEP. Sample size calculations were based on a two-sided, two- sample binomial test to compare the differences in composite endpoint proportions between the intervention arm and the standard of care arm. Since attrition is a component of the composite endpoint, attrition rates are not used as an adjustment in the power calculations. Assuming 200 subjects per group in each of the two groups (for a total of 400 subjects) and alpha set to 0.05, we have 94% power to detect a difference of 15%, assuming that 30% with a composite endpoint rate in standard of care and that 15% with endpoint in the intervention arm. We have 84% power to detect as small a difference of 13% between the two groups (i.e., 30% versus 17%).

9.5 Monitoring

The study team will review all adverse events during PrEP therapy by cumulative reports, both arms combined in aggregate, on a monthly basis. Adverse events will be graded using the ACTG toxicity grading scale and recorded using standard CCTG AE electronic data capture. The study investigators will monitor safety events in aggregate on monthly team calls. An independent Data Safety and Monitoring Board (DSMB) will not be used for this study.

9.6 Analyses

9.6.1 Statistical Analysis Plan

In general, analyses will incorporate the modified intent-to-treat (mITT) principle, namely, all randomized participants dispensed study medication will be included in the analysis. The primary analysis compares the iTAB enhanced proportion of adherence to the SOC arm.

For all secondary analyses of interest, no adjustments for multiple comparisons will be made and a p-value of 0.05 will be considered statistically significant. Demographic and baseline measurement variables will be summarized via standard descriptive statistics. There will be no interim analyses for futility or efficacy conducted.

9.6.2 Analysis of Primary Outcome

The primary analysis will use a two-sample binomial test for proportions to determine if the intervention arm will produce an improved composite endpoint rate compared to the standard of care arm. Fisher's exact test will be used along with a 95% confidence interval. As a sensitivity analysis, the two components of the composite primary endpoint will be analyzed separately (retained on PrEP and Adherence > 90%). A Fisher's exact test will be used to compare rates of study discontinuation between the active intervention arm versus standard of care arm.

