1.1.1 Hypothesis I
MSM and transgender M to F having sex with men with high risk of HIV acquisition randomized to the iTAB intervention will have higher self-reported adherence to TDF/FTC for PrEP over 48 weeks ('adherent' defined with a composite endpoint of continued retention on PrEP and \geq 90% adherence to TDF/FTC at 48 weeks) compared to MSM that have comprehensive SoC alone.

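### The primary Fisher test leaves out the site strata used in randomisation, a small gain forgone; separately, Section 9.4 gives iTAB the lower rate of a success endpoint

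*Combined protocol and SAP*

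**What the plan says.** **Site.** Section 9.3 states: "Randomization will be stratified by clinic site". The Schema and Section 3.1 agree. Section 9.6.2 specifies an unstratified comparison of two proportions: "Fisher's exact test will be used along with a 95% confidence interval". It names no method for the interval. In Section 9, stratification factors appear only in 9.6.4, as covariates for the secondary logistic models, and only if they are both unbalanced at baseline (p < 0.10) and associated with the outcome (p < 0.15). Section 9.0 says that a later SAP will override Section 9; no separate SAP text is in the documents.

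**List of sites.** Section 2.2 counts three sites, with UCLA and the Long Beach Health Department as one. Section 3.1 describes three clinics plus a fourth site at Long Beach.

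**Planning rates.** Section 9.4 states its aim as to "compare the proportion of subjects that reach the composite endpoint, defined as: continued retention and adherence to PrEP". It then takes 200 per arm and alpha 0.05 and claims 94% power, "assuming that 30% with a composite endpoint rate in standard of care and that 15% with endpoint in the intervention arm", and 84% power for 30% versus 17%.

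**Direction.** Section 9.1: "Adherent to PrEP through 48 weeks is defined as a composite endpoint of continuing on study". Section 9.6.2 tests "to determine if the intervention arm will produce an improved composite endpoint rate compared to the standard of care arm". Hypothesis I expects that people "randomized to the iTAB intervention will have higher self-reported adherence to TDF/FTC for PrEP over 48 weeks". Section 9.6.1: "The primary analysis compares the iTAB enhanced proportion of adherence to the SOC arm".

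**The concern.** Two separate points arise.

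First, the design balances the arms within site, but the primary test does not use that. If sites differ in retention and adherence, a pooled test becomes more conservative than it need be, and the estimate is not adjusted for site. At stake are a few points of power that need no extra participants.

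Second, the composite is a success wherever it is defined, and iTAB is expected to raise it. Section 9.4 nevertheless gives iTAB the lower composite rate. Read literally, the planning case is iTAB halving success. The stated power rests on these rates, so a reader must be able to tell which outcome and which arm each one describes.

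**Working it through.** **Inputs.** From Section 9.4: 200 per arm, two-sided alpha 0.05, rates 30% v 15% and 30% v 17%, stated power 94% and 84%. From Section 9.3: strata are clinic sites. The documents give neither site sizes nor site rates, so every site spread below is an assumption.

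**1. Reproducing the stated power.** Exact Fisher power is the sum over all outcomes (x, y) of Bin(x; 200, p1) × Bin(y; 200, p2), counting those with two-sided Fisher p ≤ 0.05.

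- 30% v 15%: 94.03% (stated 94%). 30% v 17%: 84.47% (stated 84%).
- Size with both arms at 30% (or 70%): 3.91%. The maximum over common rates of 2% to 98% is 4.02%.

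For comparison, the uncorrected pooled normal formula is z = [|p1−p2|√n − 1.96√(2p̄q̄)] / √(p1q1 + p2q2).

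- 30% v 15%: (2.121 − 1.157)/0.581 = 1.66, power 95.2%.
- 30% v 17%: (1.838 − 1.175)/0.593 = 1.12, power 86.9%.

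The plan's figures therefore match Fisher's test (or a continuity-corrected approximation, 93.8% and 84.1%) and not the uncorrected test.

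**2. Adding site.** With a_k successes on iTAB at site k, CMH = [Σ(a_k − E_k)]² / ΣV_k, where E_k and V_k are the hypergeometric mean and variance given the site margins. No continuity correction is used. The simulation has four sites of 50 per arm, a common odds ratio, mean SoC success 70% and mean iTAB success 85% / 83%, with 200,000 runs per cell (standard error at most 0.08 points). Pairs are for 85% / 83%. The part due to site is CMH minus the pooled uncorrected test.

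| Assumed SoC success by site | Null rejection, Fisher; CMH | Fisher power | CMH power | Gain | Of which site |
|---|---|---|---|---|---|
| No differences | 3.90; 4.98 | 93.98 / 84.53 | 95.34 / 87.15 | 1.36 / 2.62 | about 0 |
| 60–80% | 3.70; 5.00 | 94.16 / 84.73 | 95.64 / 87.81 | 1.48 / 3.08 | 0.15 / 0.38 |
| 55–85% | 3.29; 4.93 | 94.51 / 85.02 | 96.19 / 88.62 | 1.68 / 3.60 | 0.37 / 0.92 |
| 40/60/85/95% (wide) | 1.98; 4.99 | 95.64 / 86.83 | 97.96 / 92.72 | 2.32 / 5.89 | 1.15 / 3.27 |

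The site layout matters little. With three near-equal sites and SoC failure rates of about 20–41%, the gain is 1.5 / 3.2 points. With four unequal sites (90, 50, 40 and 20 per arm) and SoC failure rates of 23–45%, it is 1.5 / 3.1.

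The continuity correction does matter. With no site differences and the unequal layout, corrected CMH has 93.98 / 84.44 against Fisher's 93.99 / 84.52, so the gain disappears.

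An exact conditional stratified test keeps the level guarantee (simulated size 3.8–4.0%). It gains 0.05 / 0.04 points over Fisher with no site differences, 0.51 / 1.22 at 55–85% and 1.62 / 3.89 at 40–95%.

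**3. Which rates are meant in 9.4?** Fisher's test gives the same p-value if success and failure are exchanged, or if the arms are exchanged.

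| Reading | SoC success | iTAB success | Fisher power | Favours |
|---|---|---|---|---|
| Literal | 30% | 15% / 17% | 94.0% / 84.5% | SoC |
| Rates are failures | 70% | 85% / 83% | 94.0% / 84.5% | iTAB |
| Arms swapped | 15% / 17% | 30% | 94.0% / 84.5% | iTAB |
| SoC success 30%, gain 15 / 13 points | 30% | 45% / 43% | 85.4% / 74.3% | iTAB |

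The last row falls short because the variance is larger: 0.30×0.70 + 0.45×0.55 = 0.4575, against 0.30×0.70 + 0.15×0.85 = 0.3375. It does not reproduce the stated power. Two readings both reproduce it and agree with Hypothesis I: failure rates and swapped arms.

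**The case against.** The strongest reply is that the first point is a preference. Fisher's test guarantees its level and already delivers the stated power. Most of the CMH gain comes from letting actual type I error rise from about 3.9% to about 5%, which an unstratified uncorrected test would do as well. The part due to site is under 1 point at spreads up to 55–85%, and those spreads are assumed. All of this stands, which is why the change is an improvement and not a correction. A reader might infer that ignoring the strata makes the primary test invalid; it does not, since the test only becomes more conservative as sites differ.

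A second reply is that site is already covered in 9.6.4, or will be in the SAP. Section 9.6.4 covers secondary models only, and only conditionally. The SAP's treatment of site cannot be judged from these documents, but it is a proper place for the change.

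On 9.4, a reader might infer that the 30% and 15% must be failure rates. That is the more natural reading, because SoC stays at 30% in both scenarios, but swapped arm labels fit the stated power equally well. A reader might also infer that power is overstated and the trial too small. That needs iTAB success of 45% or 43%, rates that appear nowhere in the documents and do not reproduce 94% and 84%.

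**Conclusion.** Both points hold, with different weight.

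1. **Site strata: a cheap improvement, not an error.** Fisher is valid and N=400 stands. Uncorrected CMH gains about 1 to 4 points under none to moderate assumed site differences, with about 0 to 1 point due to stratification itself. The wide-spread case shows that this range is not a ceiling. The price is the loss of Fisher's level guarantee.
2. **Section 9.4: wrong as written.** The lower rate of a success-defined composite is placed on the arm expected to do better. The documents do not settle whether the outcome or the arms are mislabelled. Under either of those readings the 94% and 84% and the sample size are unchanged, so this is an error of statement and does not show a shortfall in size.

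**What to change.** **Section 9.6.2 and the SAP.** First reconcile Sections 2.2 and 3.1 and list the site strata actually used in randomisation. Then make the primary test a two-sided CMH test stratified by those sites, without continuity correction. Report the Mantel-Haenszel risk difference with its 95% confidence interval, and keep Fisher's test as a sensitivity analysis. If the team prefers a guaranteed level, use the exact conditional stratified test and accept the smaller gain. Keep N=400.

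**Section 9.4.** State which outcome (success or failure) and which arm each of the 30%, 15% and 17% belongs to. If they are failure rates, write success as 70% v 85% (83%); if the arms were swapped, write 15% (17%) SoC v 30% iTAB. Either way the 94% and 84% stay. Only if the sponsor says that 30% was SoC success with gains of 15 and 13 points should the Fisher power be restated, as about 85% and 74%.

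**Cost.** Wording in the protocol and SAP before database lock, with no new data or participants. Choosing uncorrected CMH means accepting actual type I error of about 5% in place of about 3.9%.

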9.6.3 Analysis of FTC Plasma Concentrations

With repeated qualitative FTC assays in each subject over time, adherence will be defined using a continuous and categorical metric. The percent adherence, calculated as number of detectable samples divided by total number of samples measured, will be compared between intervention and control using a two-sample t-test (or an appropriate non-parametric alternative if parametric assumptions fail). For strict mITT analyses, subjects that are missing a FTC concentration at any time point (whether due to missed visit or TDF/ FTC discontinuation) will be defined as having an undetectable FTC concentration while per protocol analyses will consider only available data (i.e., no imputation for missing values). A categorical metric of good adherence (> 90% of concentrations detectable) will be compared between intervention and control with the Fisher's exact test.

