3.3 FTC Qualitative Plasma Concentration as an Adherence Marker

Adherence to prescribed treatment can be difficult to assess. One objective way to measure recent adherence is to measure plasma drug concentrations. FTC concentrations in plasma remain detectable throughout the dosing interval. Specifically, trough concentrations of FTC are approximately 60 – 70 ng/mL, and range from 10 – 300 ng/mL between subjects [23, 24]. Peak concentrations are approximately 1300 – 1800 ng/mL, and range from 600 to 2500 ng/mL. While many factors contribute to variability in plasma concentrations, such as drug-drug interactions and genetic differences in absorption and excretion, completely undetectable plasma concentrations of FTC are physiologically implausible for patients who are adherent with their regimen. Even with the sources of variability noted above, undetectable concentrations (< 1 ng/mL) would be 60 to over 1000 times less than the expected concentration depending on the time post-dose, and can be justifiably assumed to represent missed doses rather than pharmacokinetic variability. We plan for 400 subjects and in total will have 3467 levels (an average of 8.6 per person). Samples will be stored at each study visit (weeks 4, 12 and every 12 weeks thereafter).

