5.1.3 Duration

Subjects will participate in this study until 48 weeks beyond the enrollment of the last subject with a maximum duration of 96 weeks for any subject. Subjects may receive study treatment until their last study visit.

Subjects will receive study treatment for the duration of the study unless they meet criteria for discontinuation.

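### The > 90% FTC category, if applied to available data, gets harder with every visit attended and so is biased against the better-retained arm

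*Combined protocol and SAP*

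**What the plan says.** Section 9.6.3 defines percent adherence by FTC as a ratio "calculated as number of detectable samples divided by total number of samples measured". It plans two versions. In the strict mITT version a missing concentration, "whether due to missed visit or TDF/ FTC discontinuation) will be defined as having an undetectable FTC concentration". In the other, "per protocol analyses will consider only available data (i.e., no imputation for missing values". The section then adds: "A categorical metric of good adherence (> 90% of concentrations detectable) will be compared between intervention and control", by Fisher's exact test. It does not say which version carries this cut-off. For the available-data version it gives no minimum number of samples and no fixed visit set.

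Section 3.3 sets the sampling: "Samples will be stored at each study visit (weeks 4, 12 and every 12 weeks thereafter". Section 5.1.3 limits follow-up, "with a maximum duration of 96 weeks for any subject". Elsewhere the FTC endpoints rest on fixed visits: Hypothesis II (1.1.2) asks for five of five, and 9.2.1 requires attendance at every scheduled visit.

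**The concern.** The number of samples a subject gives is itself an outcome, and the Schema says that iTAB is meant to improve it. If the chance of being classed as a good adherer depends on that number, the arms can differ when pill-taking does not.

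Two subjects show the problem. One has a detectable week-4 sample and is never seen again: 1 of 1, good. The other gives all five samples to week 48 with four detectable: 4 of 5, not good.

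The mITT version counts attendance by design, in favour of the better-retained arm. A reader will look to the available-data version to see whether the effect is pill-taking or attendance. Its category would bring attendance back with the opposite sign, and the reversal could be misread as evidence about adherence. Section 9.6.1 judges each secondary comparison at 0.05 without adjustment.

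**Working it through.** **Plan figures.** The plan states no rate or power for this analysis. Section 3.3 expects 3467 levels in 400 subjects: 3467/400 = 8.67 (printed as 8.6). Weeks 4, 12, 24, 36 and 48 give 5 samples; weeks 60, 72, 84 and 96 bring the maximum to 9. The expected total is 3467/3600 = 96% of that maximum.

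**Step 1: what the cut-off means.** For n = 1 to 10 the smallest count above 90% is n of n (9/10 is exactly 90% and fails). One undetectable sample is first tolerated at 10 of 11, which the schedule never reaches.

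**Step 2: chance of being good with k samples.** With independent samples and per-sample detection p (assumed), it is p^k.

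| k | p = 0.80 | p = 0.90 | p = 0.95 |
|---|---|---|---|
| 1 | 80% | 90% | 95% |
| 2 | 64% | 81% | 90% |
| 5 | 33% | 59% | 77% |
| 9 | 13% | 39% | 63% |

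**Step 3: arm-level rates to week 48.** Assume equal p in both arms, everyone giving the week-4 sample, and an exit probability h after each of the first four visits:

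P(good) = Σ(k = 1 to 4) h(1-h)^(k-1) p^k + (1-h)^4 p^5

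h = 0.08, 0.10 and 0.03 give 1-(1-h)^4 = 28%, 34% and 11% leaving.

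- SoC, h = 0.08, p = 0.85: 0.0680 + 0.0532 + 0.0416 + 0.0325 + 0.3179 = 51.3%.
- iTAB, h = 0.03, p = 0.85: 0.0255 + 0.0210 + 0.0173 + 0.0143 + 0.3928 = 47.1%.

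| p | iTAB, 11% leave | SoC, 28% leave | Gap | SoC, 34% leave | Gap |
|---|---|---|---|---|---|
| 0.85 | 47.1% | 51.3% | -4.2 | 52.9% | -5.8 |
| 0.95 | 78.6% | 80.6% | -1.9 | 81.3% | -2.6 |

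**Step 4: softer assumptions.**

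- Within-subject correlation: with a beta-binomial and ICC 0.5, p^k becomes the product over j = 0 to k-1 of (p+j)/(1+j). The gaps shrink to -1.4 and -2.0 points (p = 0.85) and -0.6 and -0.8 (p = 0.95).
- Smaller retention gap (15% v 10% leaving), independent samples: -1.2 points (p = 0.85) and -0.6 (p = 0.95).

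**Step 5: a second exit pattern.** Take retention of 85% v 70%, with leavers spread evenly over 1 to 4 samples. At p = 0.90 the better-retained arm shows 61.8% v 64.5%, or -2.7 points (-1.6 to -3.9 for p from 0.95 to 0.80). With 200 per arm, the chance of a nominally significant result against that arm is 6% to 13%, where 2.5% is intended. If every completer gave nine samples, the gap would be -3.8 to -6.8 points. Counting missing as undetectable instead gives 0.85 × 0.59 = 50.2% v 0.70 × 0.59 = 41.3% at p = 0.90, so the same data read +8.9 points.

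**Step 6: the continuous percentage.** Its expectation does not depend on k when a subject's detection is constant over time. If detection starts at 95% and falls 3 points per visit (assumed), the gap at 85% v 70% retention is -0.6 points to week 48 and -1.5 to week 96. Subjects with no sample drop out altogether, so a difference between leavers and stayers can also enter there.

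**Step 7: does a sample-level comparison cure it?** Assume that 72% stay in either arm (detection 90%), 17% stay only under iTAB, and 11% leave in either arm. The last two groups have detection q, and leavers average 2.5 samples. At q = 0.6, pooled over visits:

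- iTAB: (3.24 + 0.51 + 0.165)/(3.60 + 0.85 + 0.275) = 82.9%.
- SoC: (3.24 + 0.42)/(3.60 + 0.70) = 85.1%, so the gap is -2.3 points.

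For q from 0.8 to 0.6 the pooled gap is -0.8 to -2.3 points, against -4.2 to -4.7 for the category. At week 48 alone the sample-level gap is -1.9 to -5.7, so the pooled arm effect is the one to report. The continuous percentage has no gap in this scenario.

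**The case against.** **The cut-off may be meant for mITT only.** Section 9.6.1 makes mITT the general rule, and 9.6.3 never expressly attaches the category to available data. That is fair. But the sentence follows both versions without restriction, so an analyst could apply it to either. Section 9.0 leaves detail to a formal SAP that takes precedence, which is the place to settle it.

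**Only a supportive analysis is involved, and two versions already bracket the missing data.** The first half stands. The second does not rescue the category, because each version mixes in attendance, with opposite signs.

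**The size rests on assumptions.** This stands. A retention gap of 17 to 23 points is larger than the 15-point difference in the whole composite used for power in 9.4, and repeated samples from one person are not independent. Hence the lower range in Step 4.

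**A GEE also conditions on attendance.** This stands too: Step 7 shows a smaller bias when pooled, not none.

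**Stronger readings that the documents do not support.**

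- A reader might infer that the better-retained arm will look worse. It need not: detection of 95% v 90% with retention of 85% v 70% still shows +14.4 points at week 48, against +17.2 with equal retention.
- A reader might infer that the continuous percentage has the same fault. Under constant detection it does not (Step 6).
- A reader might infer that someone who stops drug after two detectable samples but keeps attending scores 2 of 5. Section 9.6.3 lists discontinuation as a cause of a missing concentration, which would give 2 of 2. Section 6.4 stops dried blood spots and medication monitoring off drug but does not mention plasma. The point is unsettled.

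**Conclusion.** The concern holds for one metric: the > 90% category, if it is applied to available data. That it gets harder with each added sample follows from the cut-off and the schedule. The bias against iTAB needs iTAB to retain more subjects, and it is measured relative to equal per-sample detection.

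To week 48, for detection of 85% to 95%, it is about -2 to -6 points with independent samples and a 17 to 23 point retention gap. It is about -0.5 to -2 points with strong within-subject correlation or a 5-point gap. These sizes are illustrative, since the documents give neither detection rates nor retention by arm.

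The primary endpoint, the five-of-five hypothesis, endpoint 9.2.1 and the mITT FTC analysis do not have this defect. The continuous available-data percentage is biased only if detection changes over time or differs between leavers and stayers, the latter through subjects who give no sample.

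**What to change.** In 9.6.3 or the SAP:

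1. Apply the > 90% category only to the fixed set of scheduled visits, with missing counted as undetectable. To week 48 this equals five of five, so it adds no new endpoint.
2. For the available-data version, drop the category. Compare detectable yes/no at each attended scheduled visit by logistic GEE with arm, visit and site, clustered on subject. Report the arm effect pooled over visits.
3. The continuous percentage may stay alongside. Report by arm how many subjects gave no sample and how many samples each subject gave.
4. State whether samples taken after TDF/FTC discontinuation are included, and show the result both ways if they exist.
5. State the limit: the model still conditions on attendance, so it can be biased against the better-retained arm if those it retains are poorer adherers, though pooled over visits by less than the category in the case worked above.

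The cost is wording only. The samples and assays are unchanged.
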